11.3 Other Adverse Events That Require Safety Analysis

Other adverse events that require safety analysis include AEs that fall under the “Embolic and Thrombotic Events and Thrombophlebitis” SMQ category and AEs with PT “Bone pain” and ‘Hypertension’.

Similar to AESI, summary will be provided for AEs that fall under the “Embolic and Thrombotic Events and Thrombophlebitis” SMQ category by preferred term. For “Bone pain” events, number of subjects with bone pain events by worst CTCAE grade will be provided from grade 1 to grade 5. The number and percentage of subjects with bone pain occurred during the first 24 weeks and after 24 weeks will be provided. Summary statistics will also be provided for time to first bone pain, total duration of bone pain (in days), total duration of bone pain that occurred during the first 24 weeks (in days), and total duration of bone pain that occurred after 24 weeks (in days). Total duration of bone pain is defined as sum of all bone pain duration within a subject, excluding overlapped period. Same summaries are also conducted on ‘Hypertension’.

The “Embolic and Thrombotic Events and Thrombophlebitis” SMQ category analysis will include subgroup analysis by splenectomy status, platelet above ULN, concomitant medications, and comorbidities as needed.

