10. ADVERSE EVENTS

10.1. Monitoring, Recording and Reporting of Adverse Events

An AE is any noxious, unintended, or untoward medical occurrence that may appear or worsen in a subject during the course of a study. It may be a new intercurrent illness, a worsening concomitant illness, an injury, or any concomitant impairment of the subject's health, including laboratory test values (as specified by the criteria in Section 10.3), regardless of etiology. Any worsening (ie, any clinically significant adverse change in the frequency or intensity of a pre-existing condition) should be considered an AE. A diagnosis or syndrome should be recorded on the AE page of the eCRF rather than the individual signs or symptoms of the diagnosis or syndrome.

Abuse, withdrawal, sensitivity, or toxicity to an investigational product should be reported as an AE. Overdose, accidental or intentional, whether or not it is associated with an AE should be reported on the overdose eCRF. (See Section 7.2.1.3 for the definition of overdose.) Any sequela of an accidental or intentional overdose of an investigational product should be reported as an AE on the AE eCRF. If the sequela of an overdose is an SAE, then the sequela must be reported on an SAE report form and on the AE eCRF. The overdose resulting in the SAE should be identified as the cause of the event on the SAE report form and eCRF but should not be reported as an SAE itself.

In the event of overdose, the subject should be monitored as appropriate and should receive supportive measures as necessary. There is no known specific antidote for luspatercept overdose. Actual treatment should depend on the severity of the clinical situation and the judgment and experience of the treating physician.

All subjects will be monitored for AEs during the study. Assessments may include monitoring of any or all of the following parameters: the subject's clinical symptoms, laboratory, pathological, radiological or surgical findings, physical examination findings, or findings from other tests and/or procedures.

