11.1 Adverse Events

Adverse events will be analyzed in terms of treatment-emergent adverse events (TEAEs) which are defined as any AEs that begin or worsen on or after the start of study drug through 63 days after the last dose of IP (i.e., AE start date on or after the first dose date and within last dose date + 63). In addition, an AE that occurs beyond this timeframe and that is assessed by the investigator as possibly related (suspected) to study drug will be considered as treatment-emergent.

All AEs will be coded using the Medical Dictionary for Regulatory Affairs® (MedDRA) dictionary. The incidence of TEAEs will be summarized by MedDRA system organ class (SOC) and preferred term (PT). The AE tables will be sorted by SOC and PT (within SOC) in descending frequency within the luspatercept group. If a subject experiences multiple AEs under the same PT (or SOC), then the subject will be counted only once for that PT (or SOC).

The intensity of AEs will be graded 1 to 5 according to the National Cancer Institute Common Terminology Criteria for Adverse Events (CTCAE) Version 4.0. If a subject experience the same AE more than once with different toxicity grades, then the event with the highest grade will be tabulated in “by grade” tables. In addition, AEs with a missing intensity will be presented in the summary table as an intensity category of “Missing” only if the same event category has no other valid grades.

Tables summarizing the incidence of TEAEs will be generated for each of the following by treatment group (if not otherwise specified, the summary is by SOC and PT):

- TEAEs;
- TEAEs by SOC only;
- Treatment-related TEAEs;
- Serious TEAE;
- Treatment-related serious TEAEs;
- TEAEs by CTCAE maximum severity
- Treatment-related TEAEs by CTCAE maximum severity
- TEAE with CTCAE Grade ≥ 3 ;

- Treatment-related TEAE with CTCAE Grade ≥ 3 ;
- TEAEs leading to study drug discontinuation;
- Treatment-related TEAEs leading to study drug discontinuation;
- TEAEs leading to study drug dose reduction;
- Treatment-related TEAEs leading to study drug dose reduction;
- TEAEs leading to death;
- Treatment-related TEAEs leading to death;
- Most frequent TEAEs by PT ($\geq 5\%$ in PT frequency of all subjects or subjects from any treatment group);
- Most frequent TEAEs by SOC ($\geq 5\%$ in SOC frequency of all subjects);
- Most frequent TEAEs by SOC and high level term (HLT) ($\geq 5\%$ in HLT frequency of all subjects);

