- TEAEs by Age group (≤ 32 years, > 32 years);
- TEAEs by Age group (≤ 32 years, $32-\leq 50$ years, > 50 years);
- TEAEs by Gender (male and female);
- TEAEs by Splenectomy status (Yes/No);
- TEAEs by ADA status (positive preexisting, positive treatment-emergent, negative);
- TEAE by preferred term for QTC Prolongation and Atrial Fibrillation events;
- All death by cause of death;

Listings for AEs, SAE, and AEs leading to drug discontinuation will be presented separately. Treatment-emergent AEs will be flagged in the listings. A death listing will be provided for all death events.

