11.5 Vital Sign Measurements

Vital sign is collected over time during the study. Vital sign parameters include weight, temperature, pulse rate, seated blood pressure (diastolic blood pressure [DBP] and systolic blood pressure [SBP]). The DBP and SBP are collected twice at each visit with 10 minutes apart. The average of the two assessments will be used. Summary statistics of observed values and change from baseline values will be presented for each parameter by visit by treatment group.

To further estimate the incidence of subjects whose maximum post-baseline blood pressure have passed selected criteria, summary tables representing the number and percentage of subjects with post-baseline (including ‘unscheduled’ visits) SBP/DBP assessments satisfying each criterion will be provided by treatment group. The selected criteria include below:

Maximum post-baseline SBP	No increase
	Increased < 20 mmHg
	Increased \geq 20 mmHg
	Increased \geq 20 mmHg and SBP \geq 140 mmHg
	Increased \geq 20 mmHg and SBP \geq 150 mmHg
	Subjects only with baseline values
Maximum post-baseline DBP	No increase

	Increased < 20 mmHg
	Increased \geq 20 mmHg
	Increased \geq 20 mmHg and DBP \geq 100 mmHg
	Subjects only with baseline values

A plot will be presented to show the pattern of the SBP and DBP test results over time by treatment group. Mean and SE will be presented in the plot. Additionally, a spaghetti plot for SBP and DBP values over time for individual subjects with maximum post-baseline SBP increased \geq 20 mmHg and SBP \geq 150 mmHg or maximum post-baseline DBP increased \geq 20 mmHg and DBP \geq 100 mmHg will be provided. Corresponding listing will be provided for vital sign data.

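### SAP 11.3 defines hypertension by one preferred term, so its six descriptive summaries would be incomplete for a subject if any blood-pressure AE is coded to another term

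*SAP*

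**What the plan says.** SAP 11.3 names three kinds of AE outside the AESI list that need safety analysis. Thromboembolic events are taken from a standardised MedDRA query (SMQ) and then shown by preferred term. Bone pain and hypertension are each taken by preferred term: "SMQ category and AEs with PT “Bone pain” and ‘Hypertension".

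For bone pain the section sets out subjects by worst CTCAE grade, subjects with events in and after the first 24 weeks, time to first event, and duration. Duration is calculated per subject: "Total duration of bone pain is defined as sum of all bone pain duration within a subject, excluding overlapped period". Hypertension then gets the same treatment: "Same summaries are also conducted on ‘Hypertension".

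No SMQ, high-level term (HLT) or term list is given for hypertension in 11.3. None appears in SAP 11.1, 11.2, 11.5 or 16.2, or in Protocol 9.7 or section 10.

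**The concern.** Worst grade, first onset and overlap-free duration are calculated within a subject across that subject's events. They are only as complete as the set of events that enters them. Suppose a subject's first blood-pressure AE is reported as a raised reading and coded to another term, and a later AE is coded as 'Hypertension'. Under the rule in 11.3, that subject's time to first event is too late. The duration omits the earlier episode, and the worst grade may be too low. A subject whose only blood-pressure AE carries another term does not appear in these summaries at all.

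At stake is the completeness of a descriptive analysis of an AE that the sponsor singled out for extra attention. The thromboembolic summary in the same section avoids the problem by grouping terms first.

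**Working it through.** This is a check of the text. The plan states no figure to reproduce, and no event rate is available for a calculation.

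**1. Summaries governed by the single-term rule (SAP 11.3).** Worst CTCAE grade (1) + subjects with events in the first 24 weeks and after (1) + time to first event (1) + total duration (1) + duration in the first 24 weeks (1) + duration after 24 weeks (1) = 6. All six carry over to hypertension.

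**2. What SAP 11.1 offers instead.** The section introduces its list with "Tables summarizing the incidence of TEAEs will be generated for each of the following by treatment group". The list runs to 25 tables.
- Tables giving onset or duration: 0.
- Tables giving CTCAE grade: 4. These are "TEAEs by CTCAE maximum severity", its treatment-related version, Grade 3 or higher, and its treatment-related version. All four are by system organ class (SOC) and preferred term.
- Tables pooling above preferred term but below SOC: 1, by SOC and HLT. It gives incidence only, for HLTs reaching 5% of all subjects. If all of the roughly 150 planned subjects are treated, 0.05 × 150 = 7.5, so at least 8 subjects are needed for an HLT to appear.

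**3. Cover for a blood-pressure AE coded to another term.**

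| Output | What it would show | Pooled per-subject AE grade, onset or duration? |
|---|---|---|
| SAP 11.1 SOC/preferred-term tables | Incidence and maximum grade, term by term | No |
| SAP 11.1 SOC/HLT table | Pooled incidence at 5% or more | No |
| SAP 11.1 listings ("Listings for AEs, SAE, and AEs leading to drug discontinuation will be presented separately") | Individual events | No, but could be derived by hand |
| SAP 11.5 threshold tables ("To further estimate the incidence of subjects whose maximum post-baseline blood pressure have passed selected criteria") | Categories of maximum SBP and DBP | No; readings, not AEs |
| SAP 11.5 individual plots | SBP and DBP over time, for subjects with an SBP rise of at least 20 mmHg to at least 150, or a DBP rise of at least 20 mmHg to at least 100 | No; readings, and only for the largest rises |

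Term-by-term tables cannot be added up to fill the gap. A subject with two terms is counted in two rows, and the earliest onset or the overlap between episodes cannot be recovered from counts.

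**4. Is coding to another term plausible?**
- Against: Protocol 10.1 says "A diagnosis or syndrome should be recorded on the AE page of the eCRF rather than the individual signs or symptoms", and exclusion criterion 14 (Protocol 4.3) treats hypertension as a CTCAE-graded condition.
- For: Protocol 10.1 helps only once a diagnosis has been made. Protocol 10.3 asks for a medical term instead of an abnormal result, but only for laboratory values. Blood pressure is read twice before each dose (Protocol 7.2). Protocol 6.2.1 lists a vital-sign abnormality alongside AEs as a reason for dose delay.

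Coding to another term is therefore possible, and its frequency cannot be derived from the documents.

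**The case against.** The strongest reply is that no harm is shown. The documents name no second blood-pressure term, the AE-recording rule steers sites toward the diagnosis, and a summary of one preferred term properly covers that term. A single term is also explicit and reproducible, and 11.3 uses the same rule for bone pain. Hypertension is neither an AESI in SAP 11.2 nor a protocol event of interest. SAP 11.5 examines blood pressure directly, and its individual plots show when pressure rose and for how long in the subjects with the largest rises. AE start and stop dates are collected, so a pooled analysis could be derived later.

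Much of this stands. It keeps the point small and makes the gain conditional on coding that nobody has yet checked. It does not remove the point: none of these outputs gives a pooled per-subject AE grade, onset or duration, and a grouping devised after unblinding is weaker than one fixed beforehand.

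A reader might infer that the plan undercounts hypertension, or that a blood-pressure signal would go unseen. The documents support neither reading. There is no evidence that any event is coded elsewhere. Any such event would still appear in the 11.1 tables by preferred term and in the AE listing, and measured pressures are summarised whatever the coding.

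**Conclusion.** The point holds as a conditional and minor one. The selection rule is explicit, it is narrower than the SMQ approach used in the same section for thromboembolic events, and no wider definition was found in the other safety sections. It governs all 6 planned hypertension summaries, and none of the 25 tables in SAP 11.1 supplies onset or duration.

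The number of events affected cannot be estimated and may be zero. The conclusion rests on one unverified assumption, that at least one blood-pressure AE is coded to a term other than 'Hypertension'. It also takes 11.3 at its plain meaning. The section says that the AEs needing analysis include those listed, which leaves slight room for a wider set, but it defines none, so a programmer would select one term. No endpoint, planned test, power or type I error is touched.

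**What to change.** In SAP 11.3, replace the single term with a defined group. Suggested wording: *Hypertension events are those whose preferred term is on a list fixed from blinded coded terms before unblinding. The bone-pain summaries are applied to this group and repeated for each component term, including 'Hypertension' alone.*

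The cost is one sentence, a short list and a changed selection flag, with no new data. If blinded review finds no other relevant term, the results are unchanged and their completeness is documented. The downside is that isolated high readings may be pooled with diagnosed hypertension. The component rows make that visible, and the 'Hypertension' row keeps the analysis as now planned.

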11.4 Clinical Laboratory Evaluations

Clinical laboratory data is collected by central lab and local lab. Lab data will be collected over time during the study. All summaries will be based on the SI units and missing values will not be imputed. Clinical laboratory values will be graded (grade 0-4) according to NCI-CTCAE version 4.0 for applicable tests. Normal ranges will be used to determine the “High”, “Low”, and “Normal” categories for all numeric laboratory tests. Only central lab results and local lab “Reticulocyte (Blood)” parameter will be used for table summaries.

11.4.1 Hematology/Chemistry/Immunology

The laboratory results and change from baseline will be summarized by visit by treatment group for central lab hematology and chemistry panels separately.

A shift table representing the shift from the baseline grade to maximum NCI-CTC Grades (high or low) will be provided for selected hematology and chemistry parameters having toxicity grade by visit by treatment group. The shift summary for high category will be done for hepatic function parameter (ALT, AST, ALP, total bilirubin) and renal function parameter (serum creatinine and eGFR by MDRD). The shift summary for low category will be done for hematology parameter (platelets, leukocytes and absolute neutrophil counts).

To estimate the incidence of subjects who have passed the predefined threshold for selected parameters, a summary table representing the number and percentage of subjects with lab assessments satisfying the threshold criteria will be provided by treatment group. A subject with post-baseline result (including “unscheduled” visits) meeting the criteria will be counted. The threshold criteria include below:

LIVER FUNCTION

Post-baseline Alanine Aminotransferase (ALT)	$\geq 3x$ upper limit of normal (ULN)
Post-baseline Aspartate Aminotransferase (AST)	$\geq 3x$ ULN
Post-baseline Total Bilirubin (BILTOTAL)	$\geq 2x$ ULN
Post-baseline ALT/AST and BILTOTAL	(ALT $\geq 3x$ ULN or AST $\geq 3x$ ULN) and BILTOTAL $\geq 2x$ ULN
RENAL FUNCTION	
Post-baseline eGFR by MDRD (CREATCLR)	$< 0.5x$ baseline
Post-baseline Serum Creatinine (CREAT)	$> 2x$ baseline
Albuminuria Category (ACR: mg/g)	<30
	$\geq 30 - \leq 300$
	$>300 - \leq 1000$
	$>1000 - \leq 3500$
	>3500
HEMATOLOGY	
Post-baseline Leukocytes (WBC)	$\geq 2x$ baseline and $> ULN$
	$\geq 3x$ baseline and $> ULN$
	$\geq 2x$ baseline and $> ULN$ and lasts for at least 42 days
	$\geq 3x$ baseline and $> ULN$ and lasts for at least 42 days
Maximum Post-baseline Platelets (PLAT)	$\geq 1.5x$ baseline and $> ULN$
	$\geq 600 - < 1000 \times 10^9/L$
	$\geq 1000 \times 10^9/L$

Specifically, the threshold summary for platelets will be based on the maximum post-baseline value. The summary will be provided by baseline category based on normal range (ie, within normal limit at baseline, $>$ upper limit at baseline), and by splenectomy status (Yes, No) in separate tables. Furthermore, the number and percentage of subjects with maximum post-baseline WBC exceeding $3x$ baseline value and $>ULN$, maximum post-baseline WBC exceeding $3x$ baseline value and $> ULN$ and lasts for at least 42 days, and subjects with maximum post-baseline platelets $\geq 600 - < 1000 \times 10^9/L$ and maximum post-baseline platelets exceeding $1000 \times 10^9/L$ will be provided separately by splenectomy status (Yes, No).

For some key lab parameters (ALT, AST, WBC), plots will be presented to show the pattern of the lab test values over time by treatment group. Mean and SE will be presented in the plot.

Listings of clinical laboratory data will be provided for central lab and local lab respectively for each panel in safety analysis (excluding serum erythropoietin and serum ferritin). Abnormal observations will be noted. Specifically, subjects with any WBC differential count exceeding 2x baseline value will be listed in a separate listing. All WBC differential count records of qualified subjects will be presented.

11.4.2 Serum Erythropoietin

Serum erythropoietin are collected from central laboratory. The summary of serum erythropoietin test results and change from baseline will be provided by visit by treatment group. A plot will be presented to show the pattern of the serum erythropoietin test results over time by treatment group. Mean and SE will be presented in the plot. A listing will be provided.

11.4.3 Local lab “Reticulocyte (Blood)” parameter

The “Reticulocyte (Blood)” parameter is only collected at local lab. The summary of absolute reticulocyte count and change from baseline will be provided by visit and treatment group in the same way as other lab parameters.

A line plot will be presented to show the pattern of the reticulocyte test results over time by treatment group. Mean and SE will be presented in the plot.

11.5 Vital Sign Measurements

Vital sign is collected over time during the study. Vital sign parameters include weight, temperature, pulse rate, seated blood pressure (diastolic blood pressure [DBP] and systolic blood pressure [SBP]). The DBP and SBP are collected twice at each visit with 10 minutes apart. The average of the two assessments will be used. Summary statistics of observed values and change from baseline values will be presented for each parameter by visit by treatment group.

To further estimate the incidence of subjects whose maximum post-baseline blood pressure have passed selected criteria, summary tables representing the number and percentage of subjects with post-baseline (including ‘unscheduled’ visits) SBP/DBP assessments satisfying each criterion will be provided by treatment group. The selected criteria include below:

Maximum post-baseline SBP	No increase
	Increased < 20 mmHg
	Increased \geq 20 mmHg
	Increased \geq 20 mmHg and SBP \geq 140 mmHg
	Increased \geq 20 mmHg and SBP \geq 150 mmHg
	Subjects only with baseline values
Maximum post-baseline DBP	No increase

	Increased < 20 mmHg
	Increased \geq 20 mmHg
	Increased \geq 20 mmHg and DBP \geq 100 mmHg
	Subjects only with baseline values

A plot will be presented to show the pattern of the SBP and DBP test results over time by treatment group. Mean and SE will be presented in the plot. Additionally, a spaghetti plot for SBP and DBP values over time for individual subjects with maximum post-baseline SBP increased \geq 20 mmHg and SBP \geq 150 mmHg or maximum post-baseline DBP increased \geq 20 mmHg and DBP \geq 100 mmHg will be provided. Corresponding listing will be provided for vital sign data.

11.6 Electrocardiograms

The 12-lead ECG is collected over time at selected visits. ECG parameters include heart rate, PR interval, QRS duration, RR interval and QT interval. The RR interval value will be derived per formula: RR interval (msec)=60000 (msec)/heart rate (bpm). The corrected value for QT interval will be derived based on Fridericia's formula as below:

$$\text{Fridericia's formula: } QTcF = QT / (RR)^{1/3}$$

where RR is the calculated RR interval as above

The calculated RR interval value, recorded values of ECG parameters and change from baseline values will be summarized by visit by treatment group.

To further estimate the incidence of subjects whose baseline or post-baseline QTcF values have passed the selected ICH E14 Criteria, summary tables representing the number and percentage of subjects with ECG assessments satisfying the CPMP (Committee for Proprietary Medicinal Products) criteria will be provided separately for QTcF by treatment group and visit (for baseline and post-baseline respectively). A subject with baseline or any post-baseline (including 'unscheduled' visits) result meeting individual criteria will be counted. The selected CPMP criteria includes below:

QTcF Interval	> 450 msec
	> 480 msec
	> 500 msec
QTcF Interval Increase from Baseline	\geq 30 msec
Post-baseline QTcF Interval and Increase from	Post-baseline Interval > 480 msec and

Baseline	Increase from Baseline \geq 60 msec
----------	---------------------------------------

Corresponding listing will be provided for ECG data.

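### SAP 11.6 puts RR in milliseconds into the Fridericia formula, so every QTcF comes out at one-tenth of its proper value and the QT-prolongation thresholds are effectively unreachable

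*SAP*

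**What the plan says.** All of this is in SAP Section 11.6 (Electrocardiograms).

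- RR is derived from heart rate: "The RR interval value will be derived per formula: RR interval (msec)=60000 (msec)/heart rate (bpm"). The unit is milliseconds.
- Corrected QT is attributed to Fridericia and written as QT / (RR)^(1/3). The RR to insert is then fixed in words: "where RR is the calculated RR interval as above".
- The resulting QTcF is tabulated against absolute limits of > 450, > 480 and > 500 msec. A further row, "QTcF Interval Increase from Baseline", has a limit of ≥ 30 msec. A combined row requires "Post-baseline Interval > 480 msec and" an increase of at least 60 msec.
- On counting, a subject with a baseline or any post-baseline "result meeting individual criteria will be counted".

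The section contains no division by 1000 and no statement that RR is in seconds.

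**The concern.** The Fridericia correction leaves QT unchanged at 60 bpm, which requires RR to be in seconds (RR = 1 at that rate). With RR in milliseconds the divisor at 60 bpm is 10, and QTcF becomes QT/10. The thresholds in the same section are on the ordinary millisecond scale, so the formula and the cut-offs cannot both stand.

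The failure is in the unsafe direction. A table of threshold counts shows counts, not QTcF values. If the rule were programmed as written, it would show essentially no subjects over any limit in either arm, and a reader could take that as evidence of no QT effect. The Protocol Summary lists ECG among the key safety assessments, and this is the only categorical analysis of measured QTcF that the SAP describes. The ECG is read locally (Protocol Sections 6.1, 6.2 and 6.4), and no central QTcF value is described that could serve as a cross-check.

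**Working it through.** **Inputs from SAP 11.6.** RR(msec) = 60000/HR; QTcF = QT/RR^(1/3) with that RR; limits of 450, 480, 500, +30, and 480 with +60 msec. The documents give no QTcF result to reproduce.

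**Assumptions.** The QT and heart-rate values below are illustrative and do not come from the documents. QT is taken to be in msec; the SAP states no unit for it, but all its limits are in msec.

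**Step 1: size of the error.** Write RR(msec) = 1000 × RR(sec). Then

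QT / RR(msec)^(1/3) = QT / [1000^(1/3) × RR(sec)^(1/3)] = (1/10) × QT / RR(sec)^(1/3).

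The factor is exactly 10 and does not depend on heart rate. For QT 480 at 75 bpm, RR = 60000/75 = 800 and 800^(1/3) = 9.283. As written, 480/9.283 = 51.7; with RR in seconds, 480/0.9283 = 517.1.

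**Step 2: what the limits would require.** To exceed a limit T as written, QT must exceed T × RR^(1/3). For a derived increase of 30 at a constant heart rate, QT must rise by 30 × RR^(1/3).

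| HR (bpm) | RR (msec) | QTcF for QT 500, as written | QTcF for QT 500, RR in sec | QT needed to exceed 450 as written | QT rise needed for +30 as written |
|---|---|---|---|---|---|
| 40 | 1500 | 43.7 | 436.8 | 5151 | 343 |
| 60 | 1000 | 50.0 | 500.0 | 4500 | 300 |
| 75 | 800 | 53.9 | 538.6 | 4177 | 278 |
| 100 | 600 | 59.3 | 592.8 | 3795 | 253 |
| 120 | 500 | 63.0 | 630.0 | 3572 | 238 |
| 150 | 400 | 67.9 | 678.6 | 3316 | 221 |

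Over QT 360 to 600 msec and 40 to 150 bpm, the formula as written gives about 31 to 81. With RR in seconds the range is about 315 to 814 msec.

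**Step 3: can the limits be met?** At every rate in the table, the QT needed to exceed 450 is several times the RR interval itself (4500 against 1000 at 60 bpm; 4177 against 800 at 75 bpm). If QT is no longer than RR, the largest value the written formula can give is RR/RR^(1/3) = RR^(2/3). For that to exceed 450, RR must exceed 450^(3/2) = 9546 msec, a heart rate below 60000/9546 = 6.3 bpm. The > 450 criterion therefore cannot be met, nor can the stricter > 480, > 500 and combined criteria. The ≥ 30 msec criterion is not strictly impossible, but it equals a rise of at least 300 msec in correctly scaled QTcF and is out of reach in practice.

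**The case against.** The unit slip itself is not open to dispute: the formula is legible, the text around it is not redacted, and the conversion does not appear elsewhere in the SAP. The case on the other side concerns consequence.

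- **Intent is clear.** The method is named and the limits are in msec, so an experienced programmer may divide by 1000 without being told. QTcF values near 40 would look wrong in a listing. This lowers the chance of a wrong final table, but does not make the text right. Two programmers who both follow the SAP literally would agree on the wrong value, and one who converts silently has departed from the SAP.
- **Other evidence survives.** Recorded ECG parameters, including QT and heart rate, are summarised by visit and arm in the same section. SAP 11.1 plans a separate table of treatment-emergent events for QTc prolongation, which does not use the derived variable. Both points stand, so a signal need not be lost altogether. Uncorrected QT means and investigator-reported events do not, however, replace systematic counts against QTcF limits.
- **Reach is limited.** Protocol Table 3 schedules the ECG at screening and Dose 6 Day 8 during double-blind treatment, then at Week -1 of the open-label phase (placebo subjects entering from follow-up) and 9 weeks after the last dose. QT prolongation is not among the events of special interest in SAP 11.2 or the additional events in 11.3. No efficacy endpoint, error control or dosing rule in the visible text uses QTcF. This is correct: the damage is confined to the descriptive QTcF safety output.

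**Conclusion.** The derivation is wrong as written. It understates QTcF, and any change in QTcF, by a factor of exactly 10, while the limits applied to it are on the true scale. Implemented literally, the absolute and combined criteria could not be met by any subject, and the ≥ 30 msec criterion would need a true rise of about 300 msec, so the counts would in effect be zero in both arms. Any listing or by-visit summary of QTcF would carry the same factor.

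The size of the error rests only on the SAP's own formula and on QT being in msec; the example heart rates and QT values affect only the illustrations. Whether a wrong table would actually be produced depends on the program following the text and nobody noticing. That uncertainty is no reason to leave an incorrect pre-specified safety derivation in place.

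**What to change.** In SAP Section 11.6, replace the formula with QTcF(msec) = QT(msec) / [RR(msec)/1000]^(1/3), equivalently QT(msec) / (60/HR)^(1/3), and state the units of QT and RR. Leave the thresholds as they are, and keep the RR summary in milliseconds. Check the programming specification and the code against the corrected line; a simple test is that QTcF must equal QT at 60 bpm.

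The cost is a one-line SAP correction and a program check. No efficacy analysis, data collection, sample size or clinical rule changes.
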